4.1.4.1.3 Tumour lysis syndrome

All patients have to be monitored for clinical or laboratory evidence of tumour lysis syndrome (see [Appendix 10.3](#)). To prevent tumour lysis syndrome, all patients should receive appropriate

Proprietary confidential information.

© 2018 Boehringer Ingelheim International GmbH or one or more of its affiliated companies. All rights reserved.

This document may not - in full or in part - be passed on, reproduced, published or otherwise used without prior written permission.

hydration and supportive measures (e.g. rasburicase) according to local standards or available guidelines ([R10-4517](#)). In addition, close monitoring of laboratory parameters to allow for early diagnosis of a possible tumour lysis syndrome is recommended, for details please refer to [Section 5.2.4.2](#) CTCAE version 4.03 classifies TLS in grade 3 (present), grade 4 (life threatening consequences; urgent intervention indicated) and grade 5 (death). Presence of TLS is not clearly defined by CTCAE version 4.03 ([R10-4848](#)). For this trial the Cairo-Bishop classification will be used to define presence of TLS, i.e. presence of clinical TLS ([R10-4517](#)).

4.1.4.1.4 Handling of infusion-related reactions or cytokine release syndromes

In case of an infusion-related reaction or cytokine release syndrome, appropriate measures depending on the type and severity of the reaction should be taken by the investigator according to best medical judgement and local guidelines. Supportive therapy including steroids may be used as clinically indicated. For supportive treatment of severe CRS interleukin 6 receptor (IL6R) antagonists may be used ([R15-0031](#)).

Changes of the infusion rate and temporary interruptions of the infusion have to be recorded in the eCRF.

Infusion-related reactions or cytokine release syndromes CTCAE version 4.03 grade 3 and 4 are defined to be adverse events of special interest and have to be reported according to the rules defined for SAE-reporting (see [Section 5.2.2.1](#)).

The following recommendations for the management of infusion-related reactions or cytokine release syndromes ([Table 4.1.4.1.4: 1](#)) should be considered by the investigator as guidance:

- In the case of an infusion-related reaction CTCAE version 4.03 grade 1 or 2, the infusion of BI 836909 should be temporarily interrupted and resumed as soon as considered clinically manageable by the investigator.
- In the case of an infusion-related reaction CTCAE version 4.03 grade 3 or 4, the infusion has to be stopped immediately. These patients should not be re-exposed to BI 836909.

Table 4.1.4.1.4: 1 Grading and management of cytokine release syndrome

| CRS grade | Description of severity ^a (CTCAE v4) | Interruption | Minimum expected intervention | Re-start guidance | Permanent discontinuation |
|-----------|---|--|--|---|--|
| 1 | Mild reaction; infusion interruption not indicated; intervention not indicated | n/a | Administer symptomatic treatment (e.g. paracetamol/acetaminophen for fever). Monitor for CRS symptoms including vital signs and pulse oximetry at least Q2 hours for 12 h or until resolution, whichever is earlier. | n/a | n/a |
| 2 | Therapy or infusion interruption indicated but responds promptly to symptomatic treatment (e.g. antihistamines, NSAIDS, narcotics, IV fluids); prophylactic medications indicated for ≤24 h | Immediately interrupt BI 836909 until event has improved to CRS grade ≤1, but for no less than 72 h. | Administer: 
 • Symptomatic treatment (e.g. paracetamol/acetaminophen for fever) • Supplemental oxygen when oxygen saturation is <90% on room air • Intravenous fluids or low dose vasopressor for hypotension when systolic blood pressure is <85 mmHg. Persistent tachycardia (e.g. >120 bpm) may also indicate the need for intervention for hypotension. Monitor for CRS symptoms including vital signs and pulse oximetry at least Q2 hours for 12 hours or until resolution to CRS grade ≤1, whichever is earlier. Investigators may also use tocilizumab ^c as an additional therapy in this setting at a dose of 4-8 mg/kg as a single dose, particularly if CRS does not improve to grade ≤1 within 4 h after dose interruption. For subjects with extensive co-morbidities or poor performance status, manage per grade 3 CRS guidance below. | 
 • Re-start possible, if successfully managed and improvement to CRS grade ≤1 within 7 days, • Consult with Boehringer Ingelheim medical monitor first. • Hospitalization: 48 h 
 • In the event of 2 consecutive cases of CRS of grade 2, consider reducing dose to 200 µg/d for subjects originally receiving 400 µg/d • Additional measures: additional assessments and premedication as indicated in CTP | 
 • If there is no improvement to CRS ≤grade 1 within 7 days • If interruption is >14 days • In case of repeat grade 2 event despite dose reduction |

Proprietary confidential information.

© 2018 Boehringer Ingelheim International GmbH or one or more of its affiliated companies. All rights reserved.

This document may not - in full or in part - be passed on, reproduced, published or otherwise used without prior written permission.

Table 4.1.4.1.4: 1 (cont'd) Grading and management of cytokine release syndrome

| | | | | | |
|---|---|--|--|--------------------|---|
| 3 | Prolonged (e.g. not rapidly responsive to symptomatic medication and/or brief interruption of infusion); recurrence of symptoms following initial improvement; hospitalization indicated for clinical sequelae (e.g. renal impairment, pulmonary infiltrates) | Immediately interrupt/delay BI 836909 until event has improved to CRS grade ≤ 1 . | Admit to intensive care unit for close clinical and vital sign monitoring per institutional guidelines. Administer dexamethasone (or equivalent) IV at a dose maximum of 3 doses of 8 mg (24 mg/d). The dose should then be reduced step-wise. AND/OR Investigators should also consider use of tocilizumab ^c as an additional therapy in this setting at a dose of 4-8 mg/kg as a single dose. | As for CRS grade 2 | 
 • If there is no improvement to CRS \leq grade 2 within 5 days and CRS \leq grade 1 within 7 days. • In case of 2 separate grade 3 CRS events. • If interruption is >14 days |
| 4 | Life-threatening symptoms 
 • Requirement for ventilator support OR • Grade 4 organ toxicity (excluding transaminitis) per CTCAE criteria | n/a | Admit to intensive care unit for close clinical and vital sign monitoring per institutional guidelines. Administer dexamethasone (or equivalent) IV at a dose maximum of 3 doses of 8 mg (24 mg/day). Further corticosteroid use should be discussed with the Boehringer Ingelheim medical monitor. Additionally, tocilizumab ^c should be administered at a dose of 4-8 mg/kg as a single dose and may be repeated once within 24 to 48 h based on clinical assessment. | n/a | Immediately stop the infusion (if applicable) and permanently discontinue BI 836909 therapy. |

CRS = cytokine release syndrome; CTCAE = Common Terminology Criteria for Adverse Events; IV = intravenous

^a CTCAE v4 grading used, therapy adapted using the revised grading system for cytokine release syndrome ([R16-2323](#))

^b High dose vasopressors (all doses are required for ≥ 3 h): norepinephrine monotherapy ≥ 20 $\mu\text{g}/\text{min}$, dopamine monotherapy ≥ 10 $\mu\text{g}/\text{kg}/\text{min}$, phenylephrine monotherapy ≥ 200 $\mu\text{g}/\text{min}$, epinephrine monotherapy ≥ 10 $\mu\text{g}/\text{min}$; if on vasopressin, vasopressin + norepinephrine equivalent of ≥ 10 $\mu\text{g}/\text{min}$; if on combination vasopressors (not vasopressin), norepinephrine equivalent of ≥ 20 $\mu\text{g}/\text{min}$.

^c All sites will ensure that CRS rescue medications are available on-site, including corticosteroids and 2 doses of tocilizumab per study subject.

Proprietary confidential information.

© 2018 Boehringer Ingelheim International GmbH or one or more of its affiliated companies. All rights reserved.

This document may not - in full or in part - be passed on, reproduced, published or otherwise used without prior written permission.

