5.2.1.1 Dose limiting toxicity

Dose limiting toxicity (DLT) is defined as any drug-related non-haematological adverse event CTCAE version 4.03 grade 3 or higher. The following grade 3 events will not be considered

Proprietary confidential information.

© 2018 Boehringer Ingelheim International GmbH or one or more of its affiliated companies. All rights reserved.

This document may not - in full or in part - be passed on, reproduced, published or otherwise used without prior written permission.

DLT: febrile neutropenia and infection responding to antibiotic/anti-infective treatment within 48 hours, fatigue, headache, insomnia, fever, hypotension.

Laboratory parameters of grade ≥ 3 but not considered clinically relevant and/or responding to routine medical management, will not be considered dose limiting toxicities.

Additional events that are considered DLT include:

- Persistent grade 4 neutropenia or thrombocytopenia until day 56 in the absence of detectable Multiple Myeloma as it may reflect a marrow toxic effect of BI 836909.

If infusion related reactions (IRR) or cytokine release syndromes (CRS) \geq grade 2 occur or constitute DLT events the safety committee may decide to switch to step dosing for the respective and any higher dose cohort. In that case the infusion will be started at 10(-30)% of the target dose on day 1 of the course and will be escalated to the full target dose from day 9 of course 1 on for the remainder of the course. Patients will be hospitalized and pre-medicated for the dose increase the same way they are for start of treatment. Once the safety committee decides to switch to step dosing patients that may have developed DLT due to IRR or CRS events may be replaced at the respective cohort by additional patients who will receive treatment with the adapted administration schedule (step dosing).

Although hematological adverse events (e.g. anemia, thrombocytopenia, neutropenia, lymphopenia) will not be considered DLT, complications resulting from hematological events, e.g. bleeding due to thrombocytopenia or grade 4 infection due to neutropenia are classified as non-hematological adverse events and are covered by the above definition of DLT. Nevertheless, hematological adverse events will be considered for definition of the dose for further development.

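### For a mild or moderate reaction that could be labelled either IRR or CRS, Section 4.1.4.1.4 gives conflicting guidance on interrupting and restarting the infusion

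*Protocol*

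**What the plan says.** Protocol Section 4.1.4.1.4 has one lead-in for everything that follows: "The following recommendations for the management of infusion-related reactions or cytokine release syndromes", with a pointer to Table 4.1.4.1.4: 1, "should be considered by the investigator as guidance".

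The first bullet then opens "In the case of an infusion-related reaction CTCAE version 4.03 grade 1 or 2" and says that "the infusion of BI 836909 should be temporarily interrupted and resumed as soon as considered clinically manageable by the investigator". It sets no minimum hold and no other condition for restart.

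Table 4.1.4.1.4: 1 is titled for CRS only. Its grade 1 row reads "Mild reaction; infusion interruption not indicated; intervention not indicated", and the interruption column is marked as not applicable. Its grade 2 row says "Immediately interrupt BI 836909 until event has improved to CRS grade ≤1, but for no less than 72 h". Restart then depends on reaching grade 1 or below within 7 days and on consulting the sponsor's medical monitor first, with 48 h in hospital.

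Section 4.1.4.3 has a general rule for adverse events of grade 2 or higher, whether or not they are IRR or CRS: treatment pauses until the event is back at baseline or grade 1, for at most 14 days.

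**The concern.** The bullets are written for IRR and the table for CRS, yet the lead-in covers both and I found no criterion in the protocol for separating them while a continuous infusion is running. Section 2.3 says that both must be distinguished from tumour lysis syndrome, but not how to distinguish them from each other. Section 5.2.1.1 (step dosing) and the list of adverse events of special interest in Section 5.2.2.1 name them together. A site facing a mild or moderate reaction of uncertain type therefore has two sets of instructions for the same patient.

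Two things are at stake. The first is a clear bedside instruction on a safety action, including what must happen before the infusion restarts. The second is comparable delivered dose in cycle 1 between sites, in cohorts of 3 to 6 patients whose cycle 1 experience drives escalation.

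**Working it through.** **The passages side by side**

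| Event | Bullet (names IRR) | Table 4.1.4.1.4: 1 (names CRS) | Section 4.1.4.3 (any adverse event) |
|---|---|---|---|
| Grade 1 | Interrupt; resume on the investigator's judgement | Interruption not indicated | Not covered |
| Grade 2 | Interrupt; resume on the investigator's judgement; no minimum | Hold at least 72 h and until grade 1 or below; medical monitor before restart | For the events it covers, pause until baseline or grade 1; no 72 h minimum; no monitor contact |

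At grade 1 the first two columns are opposites. At grade 2 a site can satisfy the bullet while breaching the table. Which grade 2 events Section 4.1.4.3 covers is itself open: its qualifier (intolerable and not responding to management) can be read as applying to all such events or only to those not related to the drug.

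**Infusion time at stake**

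Inputs:
- 4 weeks of infusion per cycle (Synopsis; Section 4.1.4)
- 72 h minimum hold (Table 4.1.4.1.4: 1)
- at least 14 days of treatment in course 1 to be evaluable, absent a DLT (Section 4.1.4.5)
- permanent discontinuation if interruptions exceed 14 days in total per cycle (Section 4.1.4.4)

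Infusion length: 28 × 24 = 672 h. Appendix 10.2 agrees: the last on-infusion sample in cycle 1 is at 671:50, ten minutes before the stop.

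Table, one grade 2 event: 72 / 672 = 10.7% of the cycle, leaving (672 − 72) / 24 = 25 infused days. If the hold falls in week 1, it is 72 / 168 = 43% of that week. The time is not made up, because Section 4.1.4.5 keeps the scheduled end of the cycle.

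Bullet, one grade 2 event: the documents give no duration. For assumed pauses of 1, 4, 12 and 24 h, the loss is 1/672 = 0.15%, 4/672 = 0.6%, 12/672 = 1.8% and 24/672 = 3.6%. The gap from the table's minimum is then 71, 68, 60 and 48 h.

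**Does this reach the primary analysis?**

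Infused days after k holds of 72 h are 28 − 3k: 25, 22, 19 and 16 for k = 1 to 4, all evaluable. Only a fifth hold (13 infused days, 15 days off) crosses either 14-day limit. Two holds at the table's 7-day recovery limit leave 28 − 14 = 14 infused days, which still qualifies. Section 5.2.1.1 defines a DLT as a drug-related non-haematological event of grade 3 or higher, with one added haematological criterion, so a grade 1 or 2 reaction is not itself a DLT.

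**The case against.** The strongest reply is that there is no conflict on a literal reading. The bullets govern IRR, the table governs CRS, and SAP Section 7.8.1 tabulates the two separately as events of special interest. This stands as a limit: a reader might infer that the section contradicts itself for every reaction, and it does so only for one that could take either label. It does not remove the problem, because no criterion decides the label.

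The text is also guidance, set within the investigator's judgement. That softens it, but conflicting guidance on a safety action still needs repair.

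Some protection exists whatever the label. Section 4.1.4.5 has restarts take place in hospital under the investigator's supervision, interruptions are recorded in the eCRF, and SAP Section 7.7 summarises infusion days per cycle. This narrows the gap in safeguards and makes exposure differences visible. It supplies neither the 72 h minimum nor the monitor contact.

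Two stronger inferences are tempting:
- **Grade.** The table describes grade 2 as "Therapy or infusion interruption indicated but responds promptly to symptomatic treatment", so a reader might infer that pausing a grade 1 reaction, as the bullet advises, turns it into grade 2. That wording concerns whether interruption is indicated, and the bullet acts on a grade already assigned. The shift is possible but not prescribed.
- **Step dosing.** A reader might infer that the choice of passage decides the step-dosing switch. Under Section 5.2.1.1, when IRR or CRS of grade 2 or higher occurs, "the safety committee may decide to switch to step dosing for the respective and any higher dose cohort". The trigger ignores the label, a true grade 2 event meets it under either passage, and the decision is discretionary. Only a shift from grade 1 to 2 could matter, and that is not shown.

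**Conclusion.** The point holds for a grade 1 or 2 reaction that could be called IRR or CRS. At grade 1 the guidance is opposite. At grade 2 the restart conditions are incompatible, and Section 4.1.4.3 adds a third version for the events it covers. The documented size is at least 72 of 672 h (10.7% of the cycle 1 infusion) per grade 2 event under the table, against a pause of unspecified length under the bullet. The 0.15% to 3.6% range for the bullet rests wholly on assumed pauses of 1 to 24 h.

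The consequence is unclear safety guidance, with exposure and restart safeguards that can differ by site. The documents do not support a claim that the MTD analysis is compromised: 14-day evaluability is barely touched and the DLT count is not directly affected.

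**What to change.** The sponsor should reconcile the bullets in Section 4.1.4.1.4, Table 4.1.4.1.4: 1 and Section 4.1.4.3 so that each grade has one consistent interruption and restart instruction, and should state which passage governs when IRR and CRS cannot be distinguished. Grade 3 belongs in the same edit: the bullet rules out re-exposure, the table allows restart on the grade 2 terms, and Section 4.1.4.3 states permanent discontinuation and then permits continuation at the next lower tier.

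The content of each instruction is for the sponsor's clinical team; no clinical rule or grading convention is proposed here. The cost is a wording change to two sections, by amendment or clarification letter, with no new procedures or data collection.

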4.1.4.2 Continuation of Treatment during a Course

Adverse events and laboratory values will be evaluated continuously by the investigator and the sponsor. Prior to start of each new cycle of BI 863909, adverse events and safety laboratory will be assessed. To continue treatment with a further infusion of BI 863909 all of the following criteria must be met:

- (1) Neutrophils ≥ 500 / μL ($0.5 \times 10^9/\text{L}$) and platelets $\geq 25\,000$ / μL ($25 \times 10^9/\text{L}$), with or without growth factor support or transfusions.
- (2) Acceptable tolerability (in case of an adverse event at the planned start of a treatment course, patients may continue therapy only after recovery to a level which would allow further therapy, i.e. CTCAE version 4.03 grade 1 or pre-treatment value.)

A log of all patients enrolled into the study (i.e. having given informed consent) will be maintained in the ISF at the investigational site irrespective of whether they have been treated with investigational drug or not.

4.1.4.3 Dose reductions and dose delays

Related SAEs/AEs of \geq grade 2 or non-drug related SAEs/AEs of \geq grade 2 deemed intolerable by the patient or the treating physician and not responding to appropriate medical management will result in a pause until resolution to baseline or grade 1. A pause of a maximum duration of 14 days and a dose reduction to the next lower dose level is allowed if clinically indicated. Only one dose de-escalation step is allowed.

DLT events in any cycle, cases meeting the pre-defined hepatic injury criteria (ref. [5.2.2.1](#)) and infusion related reactions or cytokine release syndromes \geq grade 3 will lead to permanent discontinuation in the dose escalation phases. After recovery to baseline or grade 1 continuation of the cycle at the next lower dose tier is allowed. Only one dose de-escalation step is allowed.

CNS events \geq grade 2 irrespective of relatedness that have not resolved to baseline or grade 1 within one week despite treatment interruption will lead to permanent discontinuation in the dose escalation phase. CNS events that have resolved to baseline or grade 1 within one week can be continued at the next lower dose level. Only one dose de-escalation step is allowed.

In case of dose reductions all future courses will also be at the reduced dose level.

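### After a first grade 3 cytokine release syndrome that recovers in time, the protocol both requires permanent discontinuation and permits re-exposure

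*Protocol*

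**What the plan says.** Protocol Section 4.1.4.3 treats four kinds of event together: DLTs in any cycle, cases meeting the hepatic injury criteria, and infusion-related reactions (IRR) or CRS of grade 3 or higher. For the last two the stop sentence ends: "grade 3 will lead to permanent discontinuation in the dose escalation phases". The next sentence permits the patient to go on with the cycle one level down once the event has settled. The join between the two sentences is: "discontinuation in the dose escalation phases. After recovery to baseline or grade 1 continuation of the cycle at the next lower dose tier is allowed". The section closes with: "In case of dose reductions all future courses will also be at the reduced dose level".

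Section 4.1.4.1.4 introduces its bullets and its CRS table as guidance for the investigator. In the grade 3 row the drug is interrupted or delayed until CRS is grade 1 or lower, and the restart column says "As for CRS grade 2". The grade 2 row it points to says "Re-start possible, if successfully managed and improvement to CRS grade" 1 or lower is reached within 7 days, after consultation with the sponsor's medical monitor. The grade 3 row stops treatment permanently for slow recovery (not grade 2 or lower within 5 days and grade 1 or lower within 7 days), for an interruption longer than 14 days, or "In case of 2 separate grade 3 CRS events". The grade 4 row says "Immediately stop the infusion (if applicable) and permanently discontinue BI 836909 therapy". A separate bullet above the table says that patients with an IRR of grade 3 or 4 should not receive the drug again.

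**The concern.** CRS is an expected toxicity of this first-in-human T-cell engager, as Section 2.3 acknowledges. Whether a patient may be re-exposed after a severe episode is a patient-safety instruction, so it should have one answer. As written, two sites facing the same event could act differently and each point to protocol text in support.

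The evidence base is affected too. Section 5.2.1 defines the MTD on cycle 1 DLTs, but uses DLT-type events in later cycles to confirm it and to select the recommended dose. A patient who is stopped contributes no later cycles, whereas one who restarts may. SAP Section 7.8.1 plans separate tables for adverse events leading to dose reduction and to treatment discontinuation, so the same clinical event could fall in either.

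**Working it through.** No arithmetic applies. The check follows one patient through every current text that governs the case: a first grade 3 CRS during dose escalation, down to grade 2 or lower within 5 days and to baseline or grade 1 within 7 days, with no more than 14 days off drug.

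| Text | Result for this patient |
|---|---|
| 4.1.4.3, stop sentence | Permanent discontinuation required, with no exception for a first event or timely recovery |
| 4.1.4.3, next sentence | Cycle may go on at the next lower level |
| 4.1.4.1.4, CRS table, grade 3 row using the grade 2 restart text | Restart possible, because none of the three permanent-stop triggers is met |

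The same patient therefore comes under a required stop and a permitted restart.

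Four things in the text might have settled this, and none does.

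- **A separating condition.** The next paragraph of 4.1.4.3 shows how the protocol does this elsewhere. CNS events not resolved within one week lead to a stop, while "CNS events that have resolved to baseline or grade 1 within one week can be continued at the next lower dose level". The paragraph on grade 3 or higher CRS has no such split.
- **Phase.** The stop sentence is limited to dose escalation. The continuation sentence and the CRS table name no phase.
- **Rank.** The table is guidance and the stop sentence is worded as a requirement, but no passage states precedence. The guidance label also does nothing for the two adjacent sentences in 4.1.4.3.
- **Event type.** The bullet against re-exposure names IRR only, so for CRS the requirement to stop rests on 4.1.4.3.

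The dose on re-exposure is also unsettled. A drug-related grade 3 CRS meets the DLT definition in 5.2.1.1, since CRS is not among its listed exceptions. The option in 3.1.1 for CRS that counts as a DLT therefore reaches this patient. The dosing texts are:

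- **4.1.4.3:** next lower level, kept for all later courses.
- **3.1.1:** a safety committee option of the previous level for 4 days, then the current level to the end of the cycle.
- **4.1.4.5, general rule:** same or next lower dose after a pause under 14 days, continued in later cycles.
- **4.1.4.5, safety committee option:** later cycles of the affected patient begin at 10-30% of target, with escalation to target possible on day 9.
- **5.2.1.1:** a safety committee option of step dosing from 10(-30)% of target to full target from day 9, for the respective and higher cohorts, if IRR or CRS of grade 2 or higher occurs or is a DLT.
- **4.1.4.1.4, CRS table:** no restart dose stated for a first grade 3 event.

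A secondary point is that the continuation sentence, read literally, covers everything in the sentence before it. That includes grade 4 CRS and grade 3-4 IRR, for which the specific texts in 4.1.4.1.4 bar re-exposure.

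**The case against.** The strongest reply is the phase reading. The stop sentence is confined to dose escalation, and the protocol has patients beyond it: as many as six more are to be treated once the MTD or recommended dose is known. If continuation were meant for them, both sentences of 4.1.4.3 would have a role. This is a coherent reading and shows how the text could be repaired. It is not stated, though. Section 4.1.4.3 never mentions those patients, and the reading leaves the table, which has no phase limit, in conflict with the stop sentence during escalation.

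A second reply is that the table is discretionary guidance, needs the medical monitor's involvement, and says only that restart is possible. All of that is true. The texts allowing re-exposure are permissive, so a site that stops the patient permanently breaches none of them. A site that restarts during escalation still goes against the stop sentence.

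Third, there are safeguards: 48 hours in hospital at restart, supervised restart under 4.1.4.5, reporting of these events within 24 hours, and safety committee review across cycles. These reduce the risk of a restart but do not say whether it is allowed.

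Two stronger readings should be resisted. A reader might treat grade 4 CRS and grade 3-4 IRR as equally open, but the specific texts are explicit there and only the loose scope of one general sentence cuts against them. A reader might also tally the texts on each side as a measure of size. The texts differ in force and specificity, so a tally measures nothing.

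**Conclusion.** The contradiction is real and must be fixed. For the patient traced here, a severe-toxicity rule gives opposite instructions within one paragraph, and the guidance table sides with the permissive one. The dosing texts that would follow a restart also disagree.

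The finding rests on current protocol wording and on no numerical assumption. The part about 3.1.1 assumes that the CRS is judged drug-related, and so a DLT.

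A reader might infer that the cycle 1 DLT count or the MTD rule is compromised. The documents do not show that: the MTD is defined on DLTs observed in cycle 1, and nothing in the conflict is shown to alter that count. What can differ between patients is safety handling, later exposure, and the later-cycle DLT evidence that Section 5.2.1 brings to confirming the MTD and choosing the recommended dose.

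**What to change.** Reconcile Sections 3.1.1, 4.1.4.1.4 (bullets and table), 4.1.4.3, 4.1.4.5 and 5.2.1.1 into one rule for grade 3 or higher CRS, grade 3 or higher IRR and other DLTs. It should cover interruption, restart, dose at restart and in later cycles, and permanent discontinuation. The step-dosing texts in 4.1.4.5 and 5.2.1.1 need to be brought into that rule, because a cross-reference alone would leave the differing schemes in place.

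The rule should state the phase it applies to, including the further patients treated at the MTD or recommended dose. It should also say whether the CRS table is binding or guidance and, if guidance, which text prevails. The choice of clinical rule and dose belongs to the sponsor and the safety committee.

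The cost is protocol amendment wording and a site notification, with no extra patients or procedures.
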